16.3.4 Efficacy Analysis

16.3.4.1 Analysis of Primary Efficacy Endpoints

The primary treatment comparisons of interest are the ACR CRISS score for MT-7117 treatment group compared with placebo group at Week 52.

ACR CRISS score is a composite endpoint assessed in a 2-step process that calculates the probability of improvement for each subject ranging from 0.0 (no improvement) to 1.0 (marked improvement) refer to Appendix 4 for further details.

The primary endpoint will be summarized using descriptive statistics with interquartile range. The distribution of ACR CRISS score may not be normal distribution. For ACR CRISS score at Weeks 16, 26, 39, and 52 the comparison between MT-7117 treatment group and placebo group will be performed using this non-parametric analysis method. The point estimates and 2-sided 95% CIs and associated P-values for the difference between the treatment groups will be obtained using the Hodges-Lehman estimator corresponding to Wilcoxon's rank sum test. This non-parametric analysis will be performed with multiple imputation method, assuming missing at random. A supportive analysis will be performed at the same way for the primary endpoints using the per-protocol set (PPS). As a secondary analysis for the primary endpoint, the same analysis method will be applied to the intent to treat (ITT) population but the patients' data after taking rescue therapy will not be included. This approach will be performed to investigate a sensitivity for the primary analysis.

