3 STUDY DESIGN

3.1 Study Design

This is a Phase 2, multicenter, randomized, double-blind, placebo-controlled, parallel-group study to evaluate efficacy, safety, and tolerability of MT-7117 in subjects with dcSSc.

The duration of the study is approximately 60 weeks; screening period up to 4 weeks, double-blind treatment period of 52 weeks, and a safety follow-up period of 4 weeks after last dose.

Following completion of the all screening assessments, subjects will return to the clinical site for start of the double-blind treatment period (Visit 2, Day 1) and baseline assessments will be evaluated and confirmed the eligibility (e.g., safety assessments, ACR CRISS components, and nevi (Melanocytic Lesions) evaluation, if nevi (Melanocytic Lesions) are present.

Eligible subjects will be randomized in a 1:1 ratio to either MT-7117 at starting of [REDACTED] every day (QD) or matching placebo in a double-blind manner, stratified by autoantibody status of [REDACTED] performed at screening (positive or negative).

Study drug will be administered once daily orally in the morning with or without food.

During the double-blind treatment period, subjects will return to the clinical site and assessments will be collected as described in protocol.

The decision about dose reduction and tolerability should be made according to the pre-specified criteria and the Investigator's clinical judgment.

If a subject is experiencing intolerance to study drug, they should first be conservatively managed using standard of care and maintain the starting dose of study drug (active or placebo).

If the subject continues to present significant intolerable AEs at the following scheduled or unscheduled visit and the Investigator deems it necessary, the daily dose of study drug can be reduced from [REDACTED] QD to [REDACTED] QD while tolerability is managed with standard of care.

If the subject continues to present significant intolerable AEs at the following scheduled or unscheduled visit and the Investigator deems it necessary, the dose of study drug can be reduced from [REDACTED] QD to [REDACTED] QD.

If the subject continues to present significant intolerable AEs at the decreased dose of [REDACTED] QD and the Investigator deems it necessary, the subject may discontinue study treatment.

All dose reductions during the Treatment Period will be done in [REDACTED] decrements. Dose reductions will be conducted via the Interactive Web-based Response System (IWRS).

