3.3 Sample Size and Power Considerations

The planned sample size of 72 is expected to provide power for the comparison between MT-7117 treatment group and placebo group for ACR CRISS score at Week 52. The calculation of sample size assumes a 2-sided alpha level of 0.05 and uses EAST (Version 6.5) for Wilcoxon Mann Whitney test. The randomized 72 subjects (36 subjects for MT-7117 and 36 subjects for placebo) with a 1:1 allocation ratio would provide 80% power to detect treatment difference of 0.35 (35% improvement on MT-7117 treatment group compared to placebo group) in ACR CRISS score at Week 52 with an associated standard deviation (SD) of 0.5.

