8.2.1 Primary Efficacy Endpoint

Primary Analysis

The primary treatment comparisons of interest are the ACR CRISS score for MT-7117 treatment group compared with placebo group at Week 52. MT-7117 treatment group includes all subjects treated with MT-7117 regardless down titrated or not. The treatment MT-7117 dose level at EOT will be compared with placebo as secondary analysis.

The primary endpoint will be summarized using descriptive statistics with interquartile range. The distribution of ACR CRISS score may not be normal distribution. For ACR CRISS score at Weeks 16, 26, 39, and 52 the comparison between MT-7117 treatment group and placebo group will be performed using the non-parametric analysis method. The point estimates and 2 sided 95% CIs and associated P-values for the difference between the treatment groups will be obtained using the Hodges-Lehman estimator corresponding to Wilcoxon's rank sum test. This non-parametric analysis will be performed with multiple imputation method, assuming missing at random. A supportive analysis will be performed at the same way for the primary endpoints using the per-protocol set (PPS). As a secondary analysis for the primary endpoint, the same analysis method will be applied to the intent to treat (ITT) population but the patients' data after taking rescue therapy will not be included. This approach will be performed to investigate a sensitivity for the primary analysis.

MI Step 1: The ACR CRISS score at week 52 will be multiply imputed using Fully Conditional Specification Method methodology under MAR assumption. The imputation for the missing ACR CRISS total score at week 52 will be conducted using all visit data of all subjects with available ACR CRISS total score up to week 52. The 50 different imputed datasets will be created using the MI procedure in SAS with 2023 for seed value. The following factors will be included in the imputation model: treatment group (TRT01P), randomization strata (the baseline autoantibody status of anti-RNA Polymerase III (positive or negative)).

[REDACTED]

[REDACTED]

[REDACTED]

[REDACTED]

[REDACTED]

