MI Step 2: The imputed datasets generated with the approach described above do contain only non-missing values. Non-parametric analysis using The Hodges-Lehman estimator will be performed for ACR CRISS score on each of the 50 generated imputed datasets. The ACR CRISS score at each visit (Weeks 16, 26, 39, and 52) from two treatments groups will enter the corresponding analysis. The Location shift estimate and two-sided 95% confidence intervals will be obtained using the Hodges-Lehman estimator corresponding to Wilcoxon's rank sum test. The paired comparison between each MT-7117 dose level with placebo will also be performed using this non-parametric analysis method. The following SAS code will be used:

[REDACTED]

[REDACTED]

[REDACTED]

[REDACTED]

MI Step 3 : Finally, the MIANALYZE procedure in SAS will be applied to combine the results from these analyses to derive an overall estimate of the treatment differences at W16, ..., W52 according to the following code. In addition to the estimates, corresponding 95% confidence intervals and p-values will be calculated.

The following example SAS code will be used:

*Combine LS mean difference estimates;

[REDACTED]

[REDACTED] TDERR;
RUN;

Prespecified Subgroup Analysis

The treatment effect on the primary endpoint of CRISS score up to Week 52, the secondary endpoint of change from baseline to Week 52 in mRSS and new Revised CRISS up to Week 52 across different subgroups will be explored based on the ITT population for the following subgroups.

Baseline CRP (<6.0, >=6.0, mg/dL)

Baseline ESR (<28, >=28, mm/hr)

Baseline Platelets (<330, >=330, x10^9/L)

Baseline SSc disease duration (<=3 years, >3 and <=5)

Baseline mRSS score (<25, >=25)

[REDACTED]
[REDACTED]
[REDACTED]

Concomitant medication (MMF, no-MMF)

Concomitant medication (Immunosuppressant(IM)*, non-IM)

Baseline disease duration and concomitant medication (<2 years+MMF, <2 years+no-MMF, >=2 years+MMF, >=2 years+no-MMF)

Region (North America, Europe)

MC1R variant (number of MC1R variants, e.g. 0, 1, 2, or 3 and each MC1R variant (MC1R variant: n≥3))

[REDACTED]
[REDACTED]

Baseline %pFVC (>50% and <=80% , >80%)

*Immunosuppressant(IM): methotrexate, leflunomide, azathioprine, mycophenolate and mycophenolic acid

The impact of MT-7117 dose reduction to efficacy

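### The visible text of the primary ACR CRISS rank comparison leaves out the anti-RNA Polymerase III randomisation stratum: the test is valid, but it forgoes some power if the factor predicts CRISS

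*SAP*

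**What the plan says.** **Where the stratum appears.** SAP 3.1 says that 1:1 randomisation is "stratified by autoantibody status of" one marker, positive or negative; its name is blacked out there. SAP 8.2.1, MI Step 1, names it among the terms of the imputation model: "randomization strata (the baseline autoantibody status of anti-RNA Polymerase III (positive or negative". SAP 8.2.2 includes the same factor in the MMRM for the continuous secondary endpoints and in the model for CRISS response (score of 0.6 or more).

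**Where it does not appear.** Protocol 16.3.4.1 says that the estimate, interval and p-value are "obtained using the Hodges-Lehman estimator corresponding to Wilcoxon's rank sum test". SAP 8.2.1 repeats this, introducing it with "For ACR CRISS score at Weeks 16, 26, 39, and 52 the comparison between MT-7117 treatment group and placebo group". MI Step 2 reads "Non-parametric analysis using The Hodges-Lehman estimator will be performed for ACR CRISS score on each of the 50 generated imputed datasets" and adds "The ACR CRISS score at each visit (Weeks 16, 26, 39, and 52) from two treatments groups will enter the corresponding analysis". In MI Step 3, "the MIANALYZE procedure in SAS will be applied to combine the results from these analyses". None of these sentences names a stratum or gives a reason for leaving it out, and SAP section 10 is silent. The SAS code that follows MI Step 2 is blacked out.

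**Sizing.** SAP 3.3 "uses EAST (Version 6.5) for Wilcoxon Mann Whitney test": two-sided 5%, 36 per arm, difference 0.35, SD 0.5, power 80%.

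**The concern.** The same CRISS score is adjusted for the stratum when it is cut at 0.6 but, on the visible text, not when it is the primary endpoint. Stratified allocation balances the antibody between arms, so the treatment comparison no longer varies with chance imbalance in it. An unstratified rank test still counts the spread between strata as noise. If the antibody predicts CRISS, the true type I error falls below 5% and the trial forgoes power that a stratified test would recover. With 72 patients and no dropout allowance stated in SAP 3.3, a few points are worth having if they cost little.

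**Working it through.** **1. The plan's own figure.** Noether's formula for the Wilcoxon test under a normal shift:

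- p = Φ(0.35 / (0.5·√2)) = 0.690
- N = (1.960 + 0.842)² / (3·(p − 0.5)²) = 72.7
- power at N = 72: Φ(√216·(p − 0.5) − 1.960) = 79.6%

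The stated 80% with 72 patients reproduces, for an unstratified test.

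**2. Inputs that the documents do not give (assumed).** Share positive P = 20% or 35%; R² = share of within-arm variance explained by the stratum = 0, 5, 10 or 20%. With total SD 0.5, the gap between strata on the CRISS scale is 0.5·√(R² / (P(1 − P))):

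| R² | gap, P = 20% | gap, P = 35% |
|---|---|---|
| 5% | 0.28 | 0.23 |
| 10% | 0.40 | 0.33 |
| 20% | 0.56 | 0.47 |

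The planned treatment effect is 0.35.

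**3. Complete data.** Simulation of 72 patients, stratified blocks of 4, normal scores, total SD 0.5, difference 0 or 0.35, 20,000 trials per cell (Monte Carlo SE about 0.3 points on power). The van Elteren statistic is z = Σ w_s(W_s − E_s) / √(Σ w_s²V_s). W_s, E_s and V_s are the rank sum, its null mean and its null variance in stratum s, and w_s = 1/(N_s + 1). Results are for P = 20% / 35%:

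| R² | Wilcoxon power | van Elteren power | change (points) | Wilcoxon type I error |
|---|---|---|---|---|
| 0% | 81.2 / 81.1 | 80.7 / 80.6 | −0.5 / −0.5 | 4.8 / 5.0% |
| 5% | 81.8 / 81.7 | 82.8 / 82.7 | +1.0 / +1.0 | 4.4 / 4.6% |
| 10% | 82.2 / 82.4 | 84.7 / 84.8 | +2.5 / +2.4 | 4.1 / 3.7% |
| 20% | 83.3 / 83.9 | 88.5 / 88.7 | +5.2 / +4.8 | 3.0 / 2.8% |

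Van Elteren type I error stayed at 4.7-5.1%. Repeat simulations agreed within Monte Carlo error and put the change at R² 0% between −0.8 and 0 points. A simple approximation to the Wilcoxon type I error, 2(1 − Φ(1.96/√(1 − R²))), gives 5.0, 4.4, 3.9 and 2.8%, in line with the last column. The unstratified power does not fall as R² rises. The loss is relative to the stratified test, not to the stated 80%.

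**4. Imputed data.** Assumed 15% missing at Week 52, correlation 0.6 with one earlier visit, 20 imputations, 4,000 trials per cell. Pooled planned Hodges-Lehmann (SE taken from the CI width, assumed) against pooled van Elteren:

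- R² 0%: 75.8 / 76.4 vs 75.8 / 76.6
- R² 10%: 76.7 / 77.1 vs 79.6 / 80.3
- R² 20%: 79.5 / 79.8 vs 84.9 / 85.5

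The pattern survives imputation. This contrast also changes the source of the p-value, so step 3 is the cleaner measure of stratification alone.

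**5. Bounded score.** Step 2 of CRISS (SAP 7.1.2.1) is a logistic transform of a linear sum, and ranks do not change under it. Step 3 therefore carries over with R² read on the logit scale, apart from ties. With an assumed 5-10% of Step 1 zeros in both arms, the change was −0.4 to −0.7 points at R² 0%, +3.2 to +3.7 at 10% and +6.8 to +8.3 at 20%.

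**The case against.** **The code is hidden.** Text that was blacked out is not missing from the plan, and a stratified test may already be programmed. This stands. The certain remainder is that the prose does not say which test is primary.

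**It is not an error.** Protocol and SAP consistently describe a two-group rank comparison, the sizing uses the same test, and nothing promises adjustment in every analysis. This stands too. A reader might infer that the omission invalidates the test or inflates type I error; step 3 shows the opposite. A reader might also infer that the 80% is wrong; step 1 reproduces it.

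**The gain needs a strong factor.** At R² 10-20% the antibody must move CRISS by 0.33-0.56, about as much as the drug or more. This stands. Gains of 2 to 5 points are conditional and should not be read as expected.

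**The test and the interval may disagree.** The plan draws estimate, interval and p-value from one analysis; taking the p-value from van Elteren separates them. In bounded-score runs (8% zeros, latent difference 0.7 SD), the planned shift divided by its CI-width SE had power of 57-60% at logit SD 2 and 25-26% at logit SD 4, against 66-68% for the unstratified Wilcoxon. That shortfall comes from pooling by CI width (itself assumed), not from stratification, and lends this point no weight. A stratum-aligned shift does not cure it: van Elteren was significant while the aligned interval covered zero in about 6-8% (logit SD 2) to 22-38% (logit SD 4) of trials.

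**Dose-level comparisons.** MI Step 2 applies the same method to each dose level against placebo. Those groups may be small and are not randomised, and splitting them by stratum could leave sparse or empty cells. This stands and limits the fix.

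**Conclusion.** The point holds as one of efficiency and consistency. On the visible text the primary comparison ignores a factor that the design stratifies on and that three other models use. Assuming 20-35% positive and taking the planned SD of 0.5 at face value, stratifying changes power by about −0.8 to 0 points if the factor is not prognostic, about +1 at R² 5%, +2 to +2.5 at R² 10% and about +5 at R² 20%. The gain is probably small, because its upper part needs a stratum gap of the order of the treatment effect. The case for changing rests on the low cost and on the sponsor's own choice to stratify and adjust elsewhere. The documents do not support calling the planned test invalid or the stated power wrong, nor asserting that the programmed analysis is unstratified.

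**What to change.** In SAP 8.2.1, before database lock:

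- **MI Step 2:** for the overall MT-7117 versus placebo comparison, compute the van Elteren statistic by randomisation stratum in each of the 50 imputed datasets.
- **MI Step 3:** pool the standardised statistic by Rubin's rules with within-imputation variance 1, so total variance = 1 + (1 + 1/50)·B, where B is the between-imputation variance. Take the p-value from it.
- If the sponsor prefers to keep the unstratified test as primary, prespecify the van Elteren version as a sensitivity analysis.
- Keep the planned Hodges-Lehmann shift and interval as the descriptive estimate, and state that the interval may not agree with the test. Do not add a stratum-aligned shift.
- Leave the dose-level comparisons unstratified.
- If the blacked-out code already stratifies, add only a sentence saying so.

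Cost: a short edit, some programming, and at most about 0.8 points of power if the antibody does not predict CRISS. The per-protocol and rescue-excluded analyses are defined as using the same method, so the edit should say whether they follow.

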9.3 Inclusion Criteria

Subjects who meet all the following criteria will be considered eligible to participate in the study:

1. Must provide signed and dated informed consent form (ICF) to participate in the study. Subjects must be able to (in the judgment of the Investigator) understand the nature of the study and all risks involved with participation in the study. Subjects must be willing to cooperate and comply with all protocol restrictions and procedures including study visits.
2. Male or female age ≥ 18 years at screening with documented diagnosis of SSc, as defined using the 2013 ACR/European League Against Rheumatism (EULAR) criteria (Appendix 1).
3. Has diffuse cutaneous form of SSc according to LeRoy and Medsger's criteria (Appendix 1).
4. Disease duration ≤ 5 years from the first non-Raynaud's phenomenon manifestation.
5. Has an mRSS of 15 to 45 units at screening and have clinical skin involvement proximal and distal to the elbows, knees, or both or any truncal involvement, with or without face involvement.
6. If disease duration is > 24 months defined as time from the first non-Raynaud phenomenon manifestation, subject must fulfil at least 1 of the criteria listed below that are indicative of active disease at screening:
 - a. A documentation of new skin involvement that occurred within the past 9 months, or
 - b. Increase in mRSS ≥ 3 units within the past 9 months, or
 - c. Presence of tendon friction rubs (TFRs) or,
 - d. C-reactive protein ≥ 6 mg/L, or
 - e. Erythrocyte sedimentation rate ≥ 28 mm/hr, or
 - f. Platelet count $\geq 330 \times 10^9/L$ (330,000/microliter).

NOTE: Investigator should exclude all other acute intercurrent illness if subjects fulfilling laboratory criteria (d, e, f) only.

7. Willing to follow restrictions regarding concomitant medications that are described in Appendix 2.

8. Female subjects who are non-lactating and have a negative urine pregnancy test at baseline visit prior to receiving the first dose of study drug.
9. Female subjects of childbearing potential and male subjects with partner of childbearing potential currently using/willing to use 2 effective methods of contraception including barrier method as described in Appendix 3.

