11.3.1.1 Medications Commonly Used in Systemic Sclerosis

NSAIDs and Analgesics

Patients may be treated with NSAIDs, including cyclooxygenase-2 (COX-2) inhibitors during the study. The dose of NSAIDs should remain stable through Week 52, unless dose reduction is required for patient safety. The choice and doses of NSAIDs are at the discretion of the Investigator. For patients who receive corticosteroids and/or NSAIDs, prophylactic treatment with proton-pump inhibitors or H2-receptor blockers may be added at the Investigator's discretion, according to local standard of care. Analgesics up to the maximum recommended dose may be used as required to treat pain. However, patients should be discouraged from using analgesics, including NSAIDs, within 12 hours prior to performance of efficacy assessments at every clinic visit.

Oral, Intravenous, or Intramuscular Corticosteroids

Subjects may receive corticosteroids at a stable dose of ≤ 10 mg/day of prednisone or equivalent during the study. Increases in corticosteroid doses for chronic treatment of SSc are not allowed during the study. To treat non-SSc-related conditions, doses of oral corticosteroids up to ≤ 40 mg/day of prednisone (or equivalent) are permitted for 2 weeks. The dose of the corticosteroid should be tapered down to the previous level as rapidly as medically possible. Decreases in corticosteroid doses for safety reasons are permitted.

DMARDs/Immunosuppressive Agents

All conventional Disease-modifying anti-rheumatic drugs (DMARDs)/Immunosuppressive agents, except for the permitted Immunosuppressant Therapy listed below, must be discontinued with appropriate washout prior to the initiation of study drug as described in the Exclusion criteria (Section 9.4) and are prohibited during the study, except when given as rescue therapy as described in Section 11.3.1.2 or for other significant systemic sclerosis complications as described in Section 11.3.1.3.

Permitted Immunosuppressant Therapy

Only one of the following immunosuppressant therapy is allowed during the study. Switching and addition of an immunosuppressant therapy is not allowed during study treatment (see Section 9.4) except when given as rescue therapy as described in Section 11.3.1.2.

- Mycophenolate (up to 3 g/day)
- Mycophenolic acid (up to 2.14 g/day)
- Methotrexate (up to 25 mg/Week)
- Leflunomide (up to 20 mg/day)
- Azathioprine (up to 3 mg/kg/day)

Vaccine

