1 INTRODUCTION

This statistical analysis plan (SAP) is based on the final protocol dated 05 Mar 2020 and protocol amendment version 5.0 dated 03 Nov 2021. The plan covers statistical analysis, tabulations, and listings of the study data to assess the efficacy, safety, and PK of MT-7117 compared to placebo.

Any statistical analysis details described in this document supersede any description of statistical analysis in the protocol.

The SAP is prepared by MTPA data science and reviewed by MTPA clinical study team and MTPC data science following GLB-BST-SOP002 ver.7. The statistical analyses and production of the outputs described in the SAP will be conducted and QCed by [REDACTED] using SAS version 9.4 or higher. The final analyses and outputs will be approved by MTPC/MTPA data science.

This SAP will be finalized prior to database lock.

PGx and PD analysis results will be reported separately from the CSR.

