7.1.1.4 Prior or Concomitant Medication

Medications will be coded according to the WHO Drug Dictionary (WHO-DD) B3 MAR 2019 version or higher.

(1) Prior Medication

Any prior medication, including prescription and over-the-counter medications, taken within 30 days before screening and all SSc-related medications used since diagnosis will be recorded on the eCRF and source documents. The following information will be collected: name of medication, dose, duration, and reason for use.

(2) Concomitant Medication

Concomitant medication(s) is defined as any medication, other than study drug, which is taken during the treatment period, including prescription, over-the-counter medications, herbals, dietary supplements, and recreational drugs. All concomitant medication(s) taken while the subject is participating in the study will be recorded.

Concomitant medication(s) will be provided only if deemed necessary by the Investigator or the subject's personal physician.

Analysis rules to determine prior medications and concomitant medications

Medications with a stop date before the first date of study drug dosing will be defined as prior medications. Medications with start date or stop date on or after the first date of study drug dosing or ongoing up to week 56 will be defined as concomitant medications.

If the medication start date is incomplete, then it will be imputed as follows for the purpose of determining concomitant use:

- If the start date is completely missing, the start date will be equal to the first dose date.

However, if the stop date is not missing and is before the first dose date, then the stop date will be used instead of the start date. It will not be considered as concomitant medications.

- If the start date is missing, the first day of the month will be used.
- If the start date and month are missing, then the first day of the first month (January) will be used.

If the medication stop date is partial, then it will be imputed as follows for the purpose of determining concomitant use:

- If the stop date is completely missing and the medication is not ongoing, the stop date will be equal to the last dose date or date of completion/withdrawal, whichever is the latest.
- If the stop date is missing, the last day of the month will be used.
- If the stop date and month are missing, then the last day of the last month (December) will be used.

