8.1.6 Prior or Concomitant Medications

The prior and concomitant medications will be summarized in table separately by ATC level 2, preferred name and treatment group and presented in data listing for the SAF population.

Regarding of the concomitant medication, the dosage of the following medications which is ongoing at the time of the first dose of study drug or is started after the first dose of study drug will be descriptively summarized. Also, the duration of the medication use will be descriptively summarized. Data describing units other than "mg" or "g" will be included only in the tabulation of time period. These medication codes is attached in the Appendix 13.1. For "METHYLPREDNISOLONE" and "METHYLPREDNISOLONE SODIUM SUCCINATE", the dose multiplied by 0.8 will be used for tabulation to convert these drugs to equivalent doses of corticosteroid.

Mycophenolate (up to 3g/day)

Mycophenolic acid (up to 2.14 g/day)

Methotrexate (up to 25 mg/Week)

Leflunomide (up to 20 mg/day)

Azathioprine (up to 3 mg/kg/day)

Corticosteroid (up to \leq 40 mg/day of prednisone)

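### The SAP's baseline CRP subgroup is cut at ten times the protocol's CRP threshold, and its MMF and immunosuppressant subgroups have no date rule to keep out rescue starters

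*SAP*

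**What the plan says.** **CRP.** The Prespecified Subgroup Analysis list in SAP section 8.2.1 gives "Baseline CRP (<6.0, >=6.0, mg/dL" as the CRP split. The next two lines split ESR at 28 mm/hr and platelets at 330 x10^9/L. In protocol section 9.3, criterion 6 lists markers of active disease. Criterion 6d is "C-reactive protein ≥ 6 mg/L", 6e is "Erythrocyte sedimentation rate ≥ 28 mm/hr", and 6f is a platelet count of at least 330 x10^9/L. The protocol synopsis gives the same CRP figure and unit.

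**Medication.** The same list has "Concomitant medication (MMF, no-MMF", a parallel line for any immunosuppressant against none, and a four-way split of disease duration by MMF. A footnote names the drugs that count as immunosuppressants, including methotrexate and mycophenolate, but gives no dates. SAP section 7.1.1.4 defines concomitant medications as "Medications with start date or stop date on or after the first date of study drug dosing or ongoing up to week 56". SAP section 8.1.6, which summarises these same drugs, covers use "ongoing at the time of the first dose of study drug or is started after the first dose of study drug".

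Protocol section 11.3.1.1 says "Switching and addition of an immunosuppressant therapy is not allowed during study treatment (see Section 9.4) except when given as rescue therapy". Section 11.3.1.2 names methotrexate and mycophenolate mofetil as possible rescue for skin worsening at or after Week 26.

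**The concern.** The three laboratory subgroups appear in the same order as criteria 6d, 6e and 6f, and two of the three match exactly. They look intended to divide subjects by the protocol's own active-disease thresholds. With CRP in mg/dL, that subgroup asks a different question: it separates very high CRP from everything else, and the upper group may be nearly empty.

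The medication subgroups raise a different problem. A subgroup is interpretable as an effect modifier only if membership is fixed before treatment can influence it. Here an immunosuppressant can be added after baseline only as rescue, and the skin rescue trigger is worsening of mRSS. Change in mRSS is one of the outcomes analysed in these subgroups and is also a component of CRISS. Under the SAP's wording, worsening subjects would leave the no-MMF group and join the MMF group because of the outcome. A difference in treatment effect between the groups could not then be read as an effect of background therapy.

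**Working it through.** **CRP unit**

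- SAP cut: 6.0 mg/dL x 10 = 60 mg/L.
- Protocol criterion 6d: 6 mg/L = 0.6 mg/dL.
- Ratio: 60 / 6 = 10.

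| Marker | Protocol 9.3 | SAP 8.2.1 | Same? |
|---|---|---|---|
| CRP | 6 mg/L (6d) | 6.0 mg/dL | No, factor 10 |
| ESR | 28 mm/hr (6e) | 28 mm/hr | Yes |
| Platelets | 330 x10^9/L (6f) | 330 x10^9/L | Yes |

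The misplaced band is CRP from 6 to below 60 mg/L if the unit is applied as written. Nobody is misplaced if the data are held in mg/L and the bare number 6.0 is applied, although the reported label would then be wrong. The documents give neither the laboratory's reporting unit nor the CRP distribution.

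For illustration only, assume log-normal CRP with median m from 3 to 12 mg/L and log-SD s from 0.8 to 1.2. The expected number of 72 subjects at or above a cut c is 72 x [1 − Φ((ln c − ln m)/s)].

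- With m = 5 and s = 1.0: 30.8 subjects at 6 mg/L and 0.5 at 60 mg/L.
- Over the whole assumed range: about 14 to 58 subjects at 6 mg/L and about 0 to 6.5 at 60 mg/L.

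**Medication subgroups**

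1. The visible list attaches the word baseline to CRP, ESR, platelets, disease duration, mRSS and %pFVC. The MMF and immunosuppressant lines do not carry it.
2. Under section 7.1.1.4, a start date on or after first dose is enough to make a drug concomitant.
3. Protocol 11.3.1.1 allows a post-baseline addition only as rescue, and 11.3.1.2 names two of the subgroup drugs as rescue.
4. It follows that a subject without MMF at first dose who is rescued with it meets the SAP definition and is classed as MMF.
5. The skin trigger is an mRSS rise of at least 5 points and at least 25%. With the CRISS coefficient of −0.81 per mRSS unit, 5 points lowers the log-odds in the CRISS equation by 0.81 x 5 = 4.05. Membership would therefore be tied to the outcome itself.
6. CRISS is compared from Week 16, but skin rescue starts at or after Week 26. A Week 16 result would be split by a later event.

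The documents give no rescue rate and no share on an immunosuppressant at baseline. If a share b of 40% to 70% is assumed, and a fraction r of 5% to 20% of the others start one as rescue, the number moved is 72 x (1 − b) x r:

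- Lowest: 72 x 0.30 x 0.05 = 1.1 of 21.6 non-users.
- Highest: 72 x 0.60 x 0.20 = 8.6 of 43.2 non-users.

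**Scale of these contrasts**

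The plan's own sample size comes first. With difference 0.35, SD 0.5 and two-sided alpha 0.05, p = Φ(0.35/(0.5√2)) = 0.6897. Noether's formula gives N = (1.960 + 0.842)² / [3 x (0.6897 − 0.5)²] = 72.7, and power at 72 is 79.6%. The stated 72 and 80% are reproduced.

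At that SD and 36 per arm, the standard error of the difference between two subgroup effects is:

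- 18/18 split in each arm (assumed): √(0.25 x 4/18) = 0.236.
- 10/26 split in each arm (assumed): √(0.25 x (2/10 + 2/26)) = 0.263.

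These are normal-theory figures for an endpoint analysed by ranks. They show only that the contrasts are imprecise even with clean membership; they do not measure either defect.

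**The case against.** **On CRP.** The protocol defines no CRP subgroup. Criterion 6d is an eligibility rule applied at screening, and only when disease duration exceeds 24 months, whereas the SAP takes the last value before first dose. Even a corrected subgroup need not reproduce 6d exactly. The SAP does say "Any statistical analysis details described in this document supersede any description of statistical analysis in the protocol", and section 10 lists no CRP change. Neither proves much, because there was no protocol analysis of CRP to supersede or change. All of this stands. What remains is the pattern of three adjacent cuts, two identical to the protocol and one off by a factor of 10, with no reason given for 60 mg/L. That makes a unit slip an inference, but a strong one.

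**On medication.** Baseline use may well have been meant. Exclusion 20h uses the word concomitant for stable background therapy, SAP section 8.1.4 lists these drugs among baseline characteristics, and the word baseline in the duration-by-MMF line may govern both terms. SAP section 8.1.8 also reports rescue medication separately from concomitant medication. These points make a baseline intent plausible. None of them supplies a date rule, and section 8.1.8 tabulates rescue without removing it from the concomitant definition. An analyst who follows section 7.1.1.4 would include rescue starters.

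**On importance.** The subgroup analyses are exploratory and imprecise. That is correct and limits the weight of the point.

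**Conclusion.** Both parts hold. The CRP cut as written is 60 mg/L, ten times criterion 6d. Its practical effect runs from none (data in mg/L, bare 6.0 applied) to placing every subject with CRP from 6 to below 60 mg/L in the low group. The medication subgroups, read by the SAP's only operative definition, admit drugs started as rescue, so membership can depend on post-randomisation worsening. The size of the resulting bias cannot be derived from the documents, and the subject counts shown above rest on assumed distributions and rates.

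The reach is confined to exploratory subgroup results for CRISS, mRSS and new Revised CRISS. The primary comparison, its alpha, the sample size and the power are unaffected. The corrections should be made, because prespecification of these subgroups means little while one cut carries a doubtful unit and the membership of others is open.

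**What to change.** - Restate the CRP subgroup as below 6.0 against 6.0 or above in mg/L (equivalently 0.6 mg/dL), and state the unit of the analysis variable. If 60 mg/L was intended, say so and give the reason.
- Define the MMF, immunosuppressant and duration-by-MMF subgroups by use ongoing at first dose of study drug. State that drugs started afterwards, including rescue, do not change membership.

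The cost is two wording corrections to the SAP. Medication use and rescue start dates are already collected, so no new data are needed. Both changes should be made before database lock and unblinding, so that the choice cannot appear to be driven by results.
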